5.4 Assessment of Compliance with Study Treatment and Monitoring

Families will document daily dosing and any reaction to at-home dosing by diary logs. Central monitoring of compliance will be performed by comparing returned unused study product against the daily dosing records. Families will be provided with 24-hr emergency contact information for the site.

Doses of study product lost or destroyed at home will also be recorded in the diary logs. All unused study product should be brought back to the clinic with each visit for reconciliation of remaining capsules/sachets.

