# **10.1. STUDY TREATMENT EXPOSURE**

Study treatment exposure will be summarized by age group (4-17 years and 18-55 years), treatment (AR101 and placebo), and study period (initial escalation, up-dosing, maintenance, and overall). Due to data collection issues with the electronic diary, the main calculation of exposure will be based on in clinic dosing data and the dose level of the dispensed study medication.

Study Period	First Dose Date	Last Dose Date
Initial Escalation	Date of first in-clinic dose at Initial Escalation Day 1	Date of last in-clinic dose at Initial Escalation Day 1 or Day 2
Up-Dosing	The day following the date study product was dispensed at Initial Escalation Day 2	Date of first in-clinic dose of 300 mg at the End Up-Dosing 300 mg Visit. For subjects who do not reach the 300 mg dose: the latest of the last in-clinic dose during the Up- Dosing period or the date of last study drug administration as entered on the Early Termination CRF page.
Maintenance	The day following the date study product was dispensed at End Up-Dosing 300 mg Visit	Latest of the last in-clinic dose during the Maintenance period or the date of last study drug administration as entered on the Early Termination CRF page

First and last dose dates for each study period will be identified as follows:

The total amount of study product consumed will be calculated as the sum of in-clinic doses plus the estimated amout of doses taken at home. At-home doses will be estimated by calculating the number of days between in clinic visits multiplied by the dose amout dispensed at the previous in clinic visit. This definition assumes that the subject took all doses between visits. If possible, the data will be reviewed to determine if subjects were temporarily taken off study drug for a period of time and those days will be removed from the number of at-home doses.

The following calculations of study drug exposure will be made and summarized:

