- Duration of Exposure (days): calculated as the date of last dose of study drug minus the date of the first dose of study drug plus one during the study period, except for the Initial Escalation period, the duration of exposure will only be 1 or 2 days depending on whether drug was taken on Initial Escalation Day 1 and Initial Escalation Day 2. Duration of exposure will be summarized using descriptive statistics for continuous endpoints as well as categorically by 28 day increments for the overall treatment period: ≤ 28 days, 29 56 days, ... 337 364 days, and >364 days.
- Total dose consumed (mg): calculated as the cumulative sum of all doses taken during the study period.
- Average dose per day (mg): calculated as the total dose consumed divided by the number of days during the study period.
- Number of unsuccessful dose increases: where an unsuccessful dose increase is defined as a single in clinic dose at a higher dose level followed by an immediate return to the previous dose level or a lower dose level.
- Number of dose reductions: where a dose reduction is defined as any decrease in dose level that does not qualify as an unsuccessful dose increase.
- Maximum dose achieved (mg/day): summarized using descriptive statistics for continuous endpoints as well as categorically using all possible dose levels: 0.5, 1, 1.5, 3, 6, 12, 20, 40, 80, 120, 160, 200, 240, or 300 mg/day.
- Time to 300 mg dosing and time to 80 mg dosing for the overall treatment period using Kaplan-Meier methodology. Time will be calculated as date of the first 300 mg (or 80 mg) dose minus the first dose date +1. Subjects who do not reach the specified dose will be censored at the date of their last study drug dose.

The non-missing valid diary entries will be used to estimate at-home dosing compliance. The following measures of compliance with at-home dosing will be calculated:

- Total number of planned at-home dosing days: calculated as the number of days where a valid diary entry was made, but excluding entries where a dose was missed because of doctor's orders.
- Percentage of planned dosing days where a full or partial dose was consumed.
- Percentage of planned dosing days where a full dose was consumed.

- Percentage of planned dosing days where a partial dose was consumed.
- Percentage of planned dosing days where a dose was missed.

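### SAP 10.1 reports adherence only over days with a diary entry and counts every home dose as taken, so adherence has an unassessable, probably upward bias and total dose is an upper bound

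*SAP*

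**What the plan says.** SAP 10.1 (Study Treatment Exposure) handles dose and compliance differently.

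**Dose.** The section opens its reasoning with "Due to data collection issues with the electronic diary" and bases the main exposure calculation on in-clinic doses plus the dispensed dose level. Home doses are the days between visits times the dose dispensed at the previous visit. The SAP is open about the consequence: "This definition assumes that the subject took all doses between visits". One correction is offered: "If possible, the data will be reviewed to determine if subjects were temporarily taken off study drug for a period of time", in which case those days are removed. Average dose per day is the same total divided by days in the period.

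**Compliance.** Here the diary is the only source: "The non-missing valid diary entries will be used to estimate at-home dosing compliance". The denominator is "Total number of planned at-home dosing days: calculated as the number of days where a valid diary entry was made". Diary entries for misses ordered by a physician are then taken out of that count. The summaries built on it give the percentages of days with a full dose, a partial dose and a full-or-partial dose, and the "Percentage of planned dosing days where a dose was missed". A miss that was recorded therefore does count against the subject.

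**Returned product.** Protocol 5.4 has unused product brought back at each visit for reconciliation and states: "Central monitoring of compliance will be performed by comparing returned unused study product against the daily dosing records". SAP 10.1 uses no returned-product count, reports no diary coverage and plans no sensitivity analysis for either measure.

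**The concern.** A scheduled day with no entry leaves both the numerator and the denominator. A family that stops dosing and stops recording looks as adherent as one that does neither. The label *planned dosing days* hides this, because the quantity is really recorded days.

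The section also treats the diary inconsistently. It sets the diary aside for dose because of its data problems, then relies on it alone for compliance. As a result, a dose the diary records as missed lowers compliance but still counts as milligrams consumed, so two tables from one section can disagree about the same day.

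After the two initial escalation days, most dosing is at home, and SAP 10 names extent of exposure as one basis of the safety assessment. If adherence and dose are misstated, the report misdescribes how much product subjects received, and readers interpreting nonresponse or tolerability start from the wrong figure.

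**Working it through.** The documents give no adherence or exposure figure to reproduce. They also do not give diary coverage, the share of home doses missed, or dosing on no-entry days. All three are assumptions below, shown as ranges.

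**Adherence**

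Let c be the share of scheduled days with a valid entry, a_obs the adherence on those days (what the SAP reports), and a_miss the adherence on no-entry days.

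- True adherence = c × a_obs + (1 − c) × a_miss
- Bias of the SAP figure = (1 − c) × (a_obs − a_miss)

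True adherence when the SAP reports 95%:

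| c | a_miss = 0 | a_miss = 0.5 | a_miss = 0.95 | a_miss = 1 |
|---|---|---|---|---|
| 0.9 | 85.5% | 90.5% | 95.0% | 95.5% |
| 0.8 | 76.0% | 86.0% | 95.0% | 96.0% |
| 0.6 | 57.0% | 77.0% | 95.0% | 97.0% |

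The bias is upward only if adherence is lower on no-entry days. It is zero if gaps are unrelated to dosing, and slightly downward if every no-entry day was dosed.

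One subject on the ideal schedule (20 weeks up-dosing plus 24 weeks maintenance = 140 + 168 = 308 days; the few in-clinic dosing days are not separated out), with 250 entries and 245 doses recorded as taken:

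- SAP figure: 245/250 = 98.0%
- All 58 no-entry days missed: 245/308 = 79.5%
- All 58 no-entry days taken: (245 + 58)/308 = 303/308 = 98.4%

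**Dose**

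The ten two-week levels in Protocol Table 3-2 below 300 mg are 3, 6, 12, 20, 40, 80, 120, 160, 200 and 240 mg, summing to 881 mg. The ideal total is 14 × 881 + 168 × 300 = 12,334 + 50,400 = 62,734 mg. If a share m of scheduled milligrams is not taken and not removed as an off-drug period, the SAP total divided by the true total is 1/(1 − m):

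| m | True total (mg) | SAP total ÷ true total |
|---|---|---|
| 2% | 61,479 | 1.02 |
| 5% | 59,597 | 1.05 |
| 10% | 56,461 | 1.11 |
| 20% | 50,187 | 1.25 |

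The error goes one way only: a missed or partial home dose that is not removed always makes the SAP total too high.

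**The two measures side by side**

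Take 14 home days at 300 mg, with 10 entries showing 9 doses taken and 1 missed. The SAP reports compliance of 9/10 = 90% and a dose of 14 × 300 = 4,200 mg. The recorded miss alone caps the dose at 13 × 300 = 3,900 mg.

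**The case against.** The strongest reply is that the SAP states its assumption openly and that the diary gaps may be purely technical. If they are unrelated to dosing, the diary-only figure is unbiased. That stands: the direction is certain for total and average dose, but not for adherence. The SAP also excludes doctor-ordered misses, counts recorded misses and partial doses, lists the daily diary records, and removes off-drug periods where it can. None of this recovers a day with no entry, and the off-drug review does not reach ordinary missed or partial doses.

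A second reply is that returned product is no clean replacement. This also stands. Protocol 5.4 describes an operational comparison with dosing records, not an analysis measure. The documents do not say that return counts are in the analysis database. Home losses are recorded in the same diary logs. Product discarded or never returned would look like product taken, and partial doses do not show in a count. Return counts can support the diary estimate but should not displace it.

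A reader might also infer that the missed-dose rules, and so responder status, rest on these figures. The documents do not support that. Protocol 6.8 applies the rules during conduct, with no link to the SAP 10.1 calculations, and SAP 7.4 sets responder status from the Exit DBPCFC, with anyone lacking one a non-responder. SAP 5 lists study drug compliance as a deviation category, reviewed blinded to help define the Per Protocol population, but does not say that the SAP 10.1 percentages drive it. A difference in diary gaps between arms is possible, but nothing in the documents shows one.

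**Conclusion.** The point holds within limits. The SAP's compliance percentage is adherence among recorded days under the name of planned days. It is likely overstated, on the plausible but unproven assumption that families dose less on days they do not record. Without diary coverage, neither the direction nor the size can be checked. Total and average dose are upper bounds on scheduled home dosing, too high by 5% at 5% missed and 11% at 10% missed, with the missed share assumed.

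A reader might go further and say that both measures are certainly inflated, or that efficacy or safety rates are compromised. The first is established only for dose. On the second, the primary endpoint does not use these measures, and SAP 10.3 divides adverse event counts by subject-years at risk, not milligrams. Duration of exposure, maximum dose and time to 300 mg do not use the all-doses-taken assumption either. The effect is confined to the descriptive dose and compliance summaries. It is worth correcting because those summaries describe what was delivered and the correction is cheap.

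**What to change.** In SAP 10.1:

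1. Use all scheduled at-home calendar days, less days withheld on medical order, as the compliance denominator.
2. Report, by arm, the percentage of scheduled days with no diary entry.
3. Beside the diary-only figure, give adherence as a range: no-entry days counted as all missed, and as all taken.
4. Subtract diary-recorded missed and partial doses from total and average dose, with a stated rule for the amount credited to a partial dose. Keep the current calculation, labelled as an upper bound.
5. Where return counts are available, add a supplementary estimate of adherence and dose from dispensed minus returned product. The sponsor should first confirm whether the counts are in the database.

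The cost is SAP wording and some programming, with no new data collection for items 1 to 4. Reported adherence and dose may look lower. Return counts cannot date missed doses, show partial doses, or separate unreturned or discarded product from doses taken, so item 5 should stay supplementary.

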# 10.2. PRIOR, CONCOMITANT, AND RESCUE MEDICATIONS AND THERAPIES

All medications recorded on the Concomitant Medications CRF page and on the On-Study Rescue Medication CRF page will be coded using the World Health Organization drug dictionary (WHODRUG), June 2015 version. Medications will be listed and summarized by Anatomical Therapeutic Chemical (ATC) Level 1 and Preferred Name.

Prior medications are defined as those which are only taken prior to the date of the first dose of study drug on Day 1 (i.e, medication end date is prior to the date of first dose of study drug).

Concomitant medications are medications taken at any time during the active treatment period. Any medications recorded for which dosing began after the last dose of randomized study treatment will also be classified as concomitant medications. As needed (PRN) medications, which may or may not be taken for long periods of time, but which are prescribed to the subject for a period that overlaps with the active treatment period, will be considered concomitant medications. If it cannot be determined whether a medication was received prior to the start of study drug dosing due to partial or missing medication start and/or end dates, it will be considered a concomitant medication.

Rescue medications are any medication used to treat symptoms of an acute allergic reaction and are recorded on a separate on-study rescue medication CRF. Unless administered during a DBPCFC, each use of a rescue medication during OIT should be associated with a corresponding adverse event (AE).

Prior medications and concomitant medications excluding rescue medications will be summarized by ATC Class, Preferred Name and treatment group. Subjects will be counted no more than one time per Preferred Name and no more than one time per ATC Level 4 in the summary.

Rescue medications will be summarized by ATC Class, Preferred Name, and treatment group for the following study periods:

- Screening (excluding rescue medications taken as a result of the Screening DBPCFC)
- Screening DBPCFC, where the medication start date is during the screening period and the CRF page indicates the medication was taken as a result of DBPCFC symptoms
- Initial Escalation period or the Up-dosing period
- Maintenance period (excluding rescue medications taken as a result of the Exit DBPCFC)
- Exit DBPCFC, where the medication start date is after the start of the maintenance period and the CRF page indicates the medication was taken as a result of DBPCFC symptoms
- Overall, including all rescue medications reported on the CRF

Concomitant non-drug therapies will be listed by subject.

## **10.3. ADVERSE EVENTS**

Symptoms that are collected during in-clinic dosing visits (including DBPCFC) are not captured on the adverse event CRF page, unless the symptom is determined to be an SAE or the subject experienced an anaphylaxis episode. Thus, each of the summaries of adverse events described below will be presented in 2 different ways:

- 1. Including only events collected on the adverse event CRF page, excluding in-clinic dosing symptoms other than SAEs and anaphylaxis episodes.
- 2. Combining adverse events collected on the adverse event CRF page and dosing symptoms collected at the in-clinic dosing visits.

All reported adverse events (AEs) will be classified into System Organ Class (SOC) and Preferred Term (PT) using Medical Dictionary for Regulatory Activities (MedDRA) version 18.1.

Treatment-emergent adverse events (TEAEs) are defined as those AEs with onset after the first dose of study drug. AEs with onset prior to first dose of study drug will be included in subject listings, but not summarized. TEAEs will be summarized for the safety population by age group (4-17 years, 4-11 years, 12-17 years, 18-55 years, and 4-55 years) and by study period as follows:

- Initial Escalation: All events beginning after the first dose of study drug on Day 1 and prior to the first at-home Up-dosing administration.
- Up-dosing: All events beginning after the first dose at-home Up-dosing administration and prior to the first at-home dose of 300 mg (which starts the Maintenance Period).
- Maintenance: All events beginning after the first dose at-home dose of 300 mg, including events after the Exit DBPCFC but prior to the rollover to ARC004.
- Overall: Across initial escalation, up-dosing, and maintenance periods.

Summaries that are displayed by system organ class and preferred terms will be ordered by descending incidence of system organ class and preferred term within each system organ class. Summaries displayed by preferred term only will be ordered by descending incidence of preferred term. Summaries of the following types will be presented:

• Overall summary of number of unique TEAEs and treatment-emergent serious adverse events (TESAEs), subject incidence of TEAEs and TESAEs meeting various criteria, and exposure adjusted incidence rates of TEAEs and TESAEs

meeting various criteria, where exposure incidence rates are defined as the total number of events divided by the total number of subject-years at risk during the study period;

- Subject incidence of TEAEs by MedDRA system organ class and preferred term;
- Exposure adjusted event rates for the most frequently-occurring TEAEs (i.e., TEAEs occurring in  $\geq$  5% of the Safety Population) by MedDRA preferred term;
- Subject incidence of TEAEs by severity grade, MedDRA system organ class, and preferred term;
- Subject incidence of TEAEs related to study drug by MedDRA system organ class, and preferred term;
- Exposure adjusted event rates for the most frequently-occurring TEAEs related to study drug (i.e., related TEAEs occurring in ≥ 5% of the Safety Population) by MedDRA preferred term;
- Subject incidence of ≥ grade 3 severity TEAEs related to study drug by MedDRA system organ class and preferred term;
- Subject incidence of SAEs by MedDRA system organ class and preferred term;
- Subject incidence of TEAEs leading to discontinuation of study drug by MedDRA system organ class and preferred term;
- Subject incidence of hypersensitivity TEAEs by MedDRA system organ class and preferred term, where hypersensitivity TEAEs are those TEAEs flagged as allergic reactions;
- Subject incidence of hypersensitivity TEAEs related to study drug by MedDRA system organ class and preferred term;
- Subject incidence of TEAEs associated with an accidental food allergen exposure by MedDRA system organ class and preferred term; and
- Subject incidence of TEAEs with onset < 90 minutes after study drug dosing by MedDRA system organ class and preferred term.

At each level of summarization (e.g., any AE, system organ class, and preferred term), subjects experiencing more than one TEAE will be counted only once within each study period. In the summary of TEAEs by severity grade, subjects will be counted once at the highest severity reported at each level of summarization.

Adverse event data will be presented in data listings by age group, treatment group, subject, study period, and event. Serious AEs; severe, life-threatening, or fatal adverse events; and AEs leading to discontinuation, reduction, or interruption of the study drug will be presented in separate data listings.

## **10.4.** FOOD ALLERGY EPISODES

The occurrence of a safety event associated with accidental food ingestion will be reported as a food allergy episode, as per Section 7.3 of the protocol. Any such event that meets the definition of an SAE will also be reported as an adverse event. All reported food allergy episodes will be listed by age group, treatment group, and subject. Episodes of allergic reaction associated with foods other than peanut will be flagged.

Food allergy episode will be summarized by study period (overall, Initial Escalation, Updosing and Maintenance). For each period, the number of subjects experiencing any food allergy episode, the number of subjects experiencing a food allergy episode in response to peanut (or non-peanut), the number of episodes of each (peanut-related and non-peanut related) experienced per subject, and the total number of food allergy episodes (peanut and non-peanut related) will be summarized. The number of episodes with unscheduled clinic visits, treatment administered, or considered SAEs will also be summarized.

#### **10.5. SYMPTOMS DURING DBPCFC**

During each food challenge, the severity of pre-specified symptoms is rated as mild, moderate, severe, life-threatening, or death at each dose level of each food product. In addition, the presence of any dose-limiting symptoms is identified.

The number of subjects experiencing any dose related symptoms and the maximum severity of any symptoms will be summarized by individual dose level and overall during the Screening peanut challenge, Screening placebo challenge, Exit peanut challenge, and Exit placebo challenge for the Safety population. Subjects will be counted at most once per type of challenge and dose level for symptom severity at the most severe level recorded for that subject.

Symptoms at the Screening and Exit DBPCFCs will be listed by subject.

#### **10.6.** SYMPTOMS DURING IN-CLINIC STUDY DRUG DOSING

During each on-treatment, in-clinic study drug dosing, the severity of pre-specified symptoms is similarly rated as mild, moderate, severe, life-threatening, or death. In addition, the presence of dose-related symptoms, and/or whether the dose was tolerated is recorded for each dose.

The number of subjects experiencing any dose related symptoms during any on-treatment, in-clinic study drug dosing visit and the maximum severity of any symptoms will be

summarized at each dose level. If a subject is administered the same dose at more than one in-clinic visit (either the subject remained at the same dose as the previous visit, or a subject had a prior dose increase and subsequent dose reduction), the most severe symptoms will be summarized for that dose level.

The time from dose administration to the time of onset of the first symptom will be summarized using descriptive statistics and presented by dose level. Time from onset of the first symptom to resolution of the last symptom will be summarized similarly. If a subject receives more than one in-clinic dose at the same dose level that subject will be counted only once using the shortest time from dose administration to onset of first symptom and the longest time from onset of first symptom to resolution of last symptom.

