6.3.4 End of Up-dosing / Start of Maintenance Period Visit

The first 300 mg in-clinic dosing visit is the end of the Up-dosing Period; it is also the start of the Maintenance Period. At this visit the following procedures are to be performed in addition to those performed at the up-dosing visits:

- Complete (not just symptom-directed) physical examination, including height and weight
- Assessment of asthma control in asthmatic subjects using the Asthma Control Test questionnaire
- Urine pregnancy test, for females of childbearing potential
- Blood draw to collect samples for:
 - Peanut- and peanut-component specific IgE, total IgE, and peanut- and peanutcomponent specific IgG4 (immunoglobulin assays). The amount of blood to be taken for the immunoglobulin assays will be communicated from the central laboratory and included in the manual of procedures.
 - CBC, obtained with the same venipuncture as the blood draw for the immunoglobulin assays
 - Optional exploratory immune cell characterization by the Immune Tolerance Network (ITN). Note that these samples can be obtained with the same venipuncture as the blood draw for the immunoglobulin assays and CBC, but will require an addition volume of blood to be collected. Separate informed consent is required.

The amount of blood to be taken in total for the above assays (required immunoglobulin assays, required CBC, and optional immune cell characterization assays) will not exceed a total volume of 0.67 mL/kg in children, to a maximum of 50 mL, total, in 8 weeks. Blood draw should be collected in compliance with local laboratory guidelines and testing regulations.

- Skin prick test to peanut extract
- Review with subjects and parents or guardians teaching about food/peanut allergy according to the investigational site's established standards. This is to include at a minimum the following topics (some or all of which may be addressed in a comprehensive anaphylaxis action plan):
 - Recognition of an allergic reaction and of the symptoms of anaphylaxis
 - When and how to administer epinephrine via auto-injector

- Requirement to go to nearest emergency facility following use of epinephrine auto-injector
- Ways to minimize the risk of accidental exposure to peanut in, and outside of, the home (may be supplemented by referral to recognized food allergy organizations for access to additional learning materials)

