6.3.5 Maintenance Period Visits

The Maintenance Period begins with the first 300 mg in-clinic dosing visit.

The first visit in the Maintenance Period is to occur 2 weeks after the start of dosing at 300 mg/d; thereafter Maintenance Period visits will occur approximately every 4 weeks.

Subjects should withhold their daily home dose of study product on in-clinic dosing days, but should take all other prescribed medications as scheduled.

The following assessments/procedures are scheduled for each in-clinic dosing Maintenance visit in the CRC:

- Concomitant medication review
- Diet (food allergen exposure) history update
- Return unused sachets or capsules to the clinic at each visit
- Symptom-directed physical examination
- Pre-dose vital sign measurement (blood pressure, pulse rate, body temperature)
- PEFR (3 attempts are to be performed, and the best value taken). PEFR should be measured at the same time for each visit assessment.
- Study product administration under observation in the clinic
- Postdose vital sign measurements (blood pressure, pulse rate) within 15 to 30 minutes postdose, and at 15- to 30-minute intervals thereafter if the postdose observation period is prolonged beyond the requisite 30 minutes (see below).
- Take home sachets (or capsules, as appropriate) for daily dosing until next visit
- Monitoring for compliance
- Monitoring for adverse events, including allergic symptoms (Section 6.7 and Section 7.2)
- Subjects will be reminded to continue to follow a peanut-avoidant diet for the duration of the study.

In the event that dose reduction from the stable dose of 300 mg/d is required during the last weeks of the planned 24-week Maintenance Period, the Maintenance Period may be extended on

an individual basis up to an additional 4 weeks (to a maximum of 28 weeks) or to a maximum study duration of 68 weeks, whichever is shorter. The Exit DBPCFC must be performed by Study Week 68. Additionally, subjects must maintain a dose of 300 mg/d for at least the last 2 consecutive weeks of the Maintenance Period to qualify for the Exit DBPCFC. Failure to do so will result in the subject being discontinued from the study as a maintenance failure nonresponder for the primary and key secondary analyses.

If dosing is discontinued, the subject will be asked to return to the CRC 14 days following their last dose of AR101 to undergo an Early Discontinuation Visit (Section 6.5).

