The procedures for dose reduction and re-escalating back to a dose of 300 mg/d in the Maintenance Period will follow the same guidelines as for the Up-dosing Period.

The procedure for monitoring subjects for safety after in-clinic dosing is the same as for updosing visits (Section 6.7.3), except that the initial period of required post-dose observation may be shortened to 30 min.

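### SAP 10.6 keeps each subject's worst result over all in-clinic doses at a level, and 300 mg has about seven planned observed doses against one at most levels, so the rows are not comparable across doses

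*SAP*

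**What the plan says.** SAP 10.6 summarises, at each dose level, "The number of subjects experiencing any dose related symptoms during any on-treatment, in-clinic study drug dosing visit", together with maximum severity. Repeat doses at one level are collapsed to a single result per subject. The rule names the case in which "either the subject remained at the same dose as the previous visit", so Maintenance dosing at 300 mg falls under it, as do repeats after a dose reduction. For severity, "the most severe symptoms will be summarized for that dose level". For timing, "that subject will be counted only once using the shortest time from dose administration to onset" of the first symptom, and the longest time from first onset to last resolution. The section does not split the table by study period or visit, and sets no denominator of doses given.

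The number of observed doses per level comes from the protocol. Section 6.3.2 plans one supervised dose at each new up-dosing level. Section 6.3.4 states: "The first 300 mg in-clinic dosing visit is the end of the Up-dosing Period". Section 6.3.5 continues: "The first visit in the Maintenance Period is to occur 2 weeks after the start of dosing at 300 mg/d", and "thereafter Maintenance Period visits will occur approximately every 4 weeks"; study product is given under observation at each of these visits. The same section keeps the up-dosing safety monitoring procedure, "except that the initial period of required post-dose observation may be shortened to 30 min".

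**The concern.** Side by side, the rows invite the question of whether symptoms become more or less frequent, or more severe, as the dose rises. The number of chances to record a symptom changes along that same axis. The worst of seven doses can never be milder than the first 300 mg dose, which is the like-for-like comparator for a one-dose row at 240 mg. Part of any rise at 300 mg could therefore come from the number of looks, and a real fall could be hidden. This is the target maintenance dose, and Protocol 1.2.1 reports that symptoms tended to diminish with longer treatment in earlier trials. At stake is the reading of one descriptive safety table across dose levels, for children and adults alike.

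**Working it through.** **Check on the schedule.** The up-dosing table has 11 levels (3 to 300 mg). The 3 mg level is first dosed in clinic during Initial Escalation, which leaves 11 − 1 = 10 up-dosing visits. At 2-week steps that is 20 weeks. Both figures match Protocol 6.3.2.

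**Planned observed doses per level.**

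- 0.5, 1 and 1.5 mg: one each, on Day 1 (Protocol 6.3.1.1).
- 3 mg: Day 1 and Day 2 (6.3.1.1, 6.3.1.2) = 2.
- 6 mg: Day 1 and the first up-dosing visit = 2.
- 12 to 240 mg: 1 each.
- 300 mg: end of up-dosing (week 0) plus Maintenance weeks 2, 6, 10, 14, 18 and 22 = 7. It is 8 if Maintenance runs to 28 weeks, which Protocol 3.2 allows.

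So 11 of 14 levels have one planned observed dose. These are minimums, because holds and reductions add repeats at lower levels too.

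**Effect on incidence.** Assume per-dose risk p, the same at every dose. With independent doses, P(any symptom in k doses) = 1 − (1 − p)^k. With within-subject correlation I use a beta-binomial with a = p(1 − ICC)/ICC and b = (1 − p)(1 − ICC)/ICC, so that P(any) = 1 − B(a, b + k)/B(a, b). Neither p nor ICC is in the documents, so both are assumed over a range. For k = 7:

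| p (one-dose row) | independent | ICC 0.2 | ICC 0.5 | ICC 0.8 |
|---|---|---|---|---|
| 2% | 13.2% | 8.4% | 5.1% | 3.0% |
| 5% | 30.2% | 20.0% | 12.3% | 7.5% |
| 10% | 52.2% | 36.5% | 23.5% | 14.7% |
| ratio to p | 5.2 to 6.6 | 3.7 to 4.2 | 2.3 to 2.5 | 1.5 |

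The same formula applies to any severity threshold. If moderate or worse symptoms occur at 1% of doses, the 300 mg row reads 6.8%, 4.3%, 2.6% or 1.5% across the same columns.

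**How far risk must fall to cancel this.** For the seven-dose row merely to equal a one-dose row at 10%, the per-dose risk at 300 mg would have to be 1.5% (independent), 2.4% (ICC 0.2), 4.0% (ICC 0.5) or 6.7% (ICC 0.8).

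With independent doses and a risk that falls by a factor r at each visit, the row reads 1 − ∏(1 − p·r^j), j = 0 to 6:

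- p = 10%, r = 0.8: 33.6%.
- p = 10%, r = 0.5: 18.6%.
- p = 5% at the first 300 mg dose, r = 0.5: 9.6%, slightly below a 10% row at 240 mg.

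**Effect on timing.** Times exist only for symptomatic doses, so what matters is the number n of symptomatic doses a subject has. As an illustration, take lognormal times with median 30 minutes and log-SD 0.7, independent across doses. The median shortest is 30·exp(0.7·Φ⁻¹(1 − 0.5^(1/n))) and the median longest is 30·exp(0.7·Φ⁻¹(0.5^(1/n))):

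- n = 1: 30 and 30 minutes.
- n = 2: about 20 and 44.
- n = 3: about 17 and 53.
- n = 7: about 12 and 75.

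With independent doses at p = 2, 5 and 10%, subjects with any symptom average 7p/[1 − (1 − p)^7] = 1.06, 1.16 and 1.34 symptomatic doses. The median shortest time is then about 29, 28 and 26 minutes and the longest about 31, 32 and 34. The timing bias is small in that case and grows if reactions cluster within subjects. Incidence behaves the other way: its inflation is largest when doses are independent.

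**The case against.** Worst-per-subject is a normal, conservative safety convention. SAP 10.3 counts subjects at their highest severity and SAP 10.5 does the same for the food challenge. It answers a fair question: did this subject ever react at this level, and how badly? SAP 10.6 plans no trend test, and placebo follows the same visit schedule, so a concurrent control stands beside each 300 mg figure. SAP 10.3 also repeats its adverse event summaries with in-clinic symptoms included, split by Initial Escalation, Up-dosing and Maintenance, with some exposure-adjusted rates.

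Much of this stands. The worst-ever table has a use and should not be lost: dropping it would remove maximum severity at the Maintenance doses from 10.6. The comparison between arms at 300 mg is on an equal schedule, although the size of both rates depends on the number of doses. What does not stand is the idea that SAP 10.3 repairs the problem, because none of its listed summaries is by dose level. In SAP 10.5 the rule does no harm, because doses are not repeated within a challenge. For vital signs, SAP 10.10 meets the same repeat-dose situation by giving the repeat visit its own summary; 10.6 pools instead.

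A reader might infer that symptoms must appear to worsen at 300 mg. The documents do not support that. Only subjects who tolerated earlier levels reach 300 mg, risk may fall with time on treatment, and the option of a 30-minute observation at Maintenance visits may reduce symptom capture at six of the seven doses. All three work against a visible rise.

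**Conclusion.** The point holds for the comparison across dose levels in SAP 10.6. At equal per-dose risk, incidence and maximum severity at 300 mg are inflated relative to the other levels: about 1.5-fold at ICC 0.8, 2.3 to 2.5-fold at 0.5, 3.7 to 4.2-fold at 0.2, and at most 5 to 7-fold with independent doses. This rests on assumed risks of 2 to 10% and on seven planned 300 mg doses against one. Onset and resolution are biased in the same way, by an amount that depends on how many of a subject's doses are symptomatic.

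Three stronger readings should be resisted. The 5 to 7-fold figure is an upper bound, since independence is unlikely for one person's allergic reactivity. Medians of 12 and 75 minutes would require symptoms at all seven doses. And the safety profile as a whole remains interpretable: the period-based summaries in SAP 10.3 are untouched, both arms share the schedule, and efficacy is unaffected. This is a cheap improvement to one descriptive table.

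**What to change.** In SAP 10.6:

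- Base the by-dose-level comparison of incidence, maximum severity and timing on the first in-clinic dose at each level, one observation per subject per level.
- Show the 300 mg Maintenance visits, and other repeat doses, in separate rows. Give symptomatic doses over doses administered, maximum severity, and onset and resolution per dose.
- Keep the worst-ever table as a supplementary summary, labelled with the number of observed doses per level.

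The cost is a short change of SAP wording, one more table and slightly more programming. Symptoms and tolerability are already recorded for each in-clinic dose, so no new data are needed.
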